## 6.4 Reporting of serious adverse events

All SAEs have to be reported, whether or not considered causally related to the investigational product, or to the study procedure(s). All SAEs will be recorded in the CRF.

If any SAE occurs in the course of the study, then Investigators or other site personnel inform the appropriate AstraZeneca representatives within one day i.e., immediately but **no later than 24 hours** of when he or she becomes aware of it.

The designated AstraZeneca representative works with the Investigator to ensure that all the necessary information is provided to the AstraZeneca Patient Safety data entry site **within 1 calendar day** of initial receipt for fatal and life threatening events **and within 5 calendar days** of initial receipt for all other SAEs.

For fatal or life-threatening adverse events where important or relevant information is missing, active follow-up is undertaken immediately. Investigators or other site personnel inform AstraZeneca representatives of any follow-up information on a previously reported SAE within one calendar day i.e., immediately but **no later than 24 hours** of when he or she becomes aware of it.

The AstraZeneca representative will advise the Investigator/study site staff how to proceed.

## 6.5 Overdose

- An overdose with associated AEs is recorded as the AE diagnosis/symptoms on the relevant AE modules in the CRF and on the Overdose CRF module.
- An overdose without associated symptoms is only reported on the Overdose CRF module.

If an overdose on an AstraZeneca study drug occurs in the course of the study, then the Investigator or other site personnel inform appropriate AstraZeneca representatives immediately, or **no later than 24 hours** of when he or she becomes aware of it.

If an overdose is suspected, monitoring of vital functions as well as treatment should be performed as appropriate.

The designated AstraZeneca representative works with the Investigator to ensure that all relevant information is provided to the AstraZeneca Patient Safety data entry site.

For overdoses associated with a SAE, the standard reporting timelines apply, see Section 6.4. For other overdoses, reporting must occur within 30 days.

## 6.6 Pregnancy

All pregnancies and outcomes of pregnancy should be reported to AstraZeneca except for:

- If the pregnancy is discovered before the study subject has received any study drug

### 6.6.1 Maternal exposure

If a subject becomes pregnant during the course of the study investigational product should be discontinued immediately.

Pregnancy itself is not regarded as an adverse event unless there is a suspicion that the investigational product under study may have interfered with the effectiveness of a contraceptive medication. Congenital abnormalities/birth defects and spontaneous miscarriages should be reported and handled as SAEs. Elective abortions without complications should not be handled as AEs. The outcome of all pregnancies (spontaneous miscarriage, elective termination, ectopic pregnancy, normal birth or congenital abnormality) should be followed up and documented even if the subject was discontinued from the study.

If any pregnancy occurs in the course of the study, then the Investigator or other site personnel informs the appropriate AstraZeneca representatives within 1 day i.e., immediately but **no later than 24 hours** of when he or she becomes aware of it.

The designated AstraZeneca representative works with the Investigator to ensure that all relevant information is provided to the AstraZeneca Patient Safety data entry site within 1 or 5 calendar days for SAEs (see Section 6.4) and within 30 days for all other pregnancies.

The same timelines apply when outcome information is available.

## 6.7 Medication Error

For the purposes of this clinical study a medication error is an unintended failure or mistake in the treatment process for an AstraZeneca study drug that either causes harm to the subject or has the potential to cause harm to the subject.

A medication error is not lack of efficacy of the drug, but rather a human or process related failure while the drug is in control of the study site staff or subject.

Medication error includes situations where an error.

- occurred
- was identified and intercepted before the subject received the drug
- did not occur, but circumstances were recognize that could have led to an error

Examples of events to be reported in clinical studies as medication errors:

- Drug name confusion
- Dispensing error e.g. medication prepared incorrectly, even if it was not actually given to the subject
- Drug not administered as indicated, for example, wrong route or wrong site of administration
- Drug not taken as indicated e.g. tablet dissolved in water when it should be taken as a solid tablet
- Drug not stored as instructed e.g. kept in the fridge when it should be at room temperature

Examples of events that **do not** require reporting as medication errors in clinical studies:

- Subject accidentally missed drug dose(s) e.g. forgot to take medication
- Accidental overdose (will be captured as an overdose)
- Subject failed to return unused medication or empty packaging
- Errors related to background and rescue medication, or standard of care medication in open label studies, even if an AZ product

Medication errors are not regarded as AEs but AEs may occur as a consequence of the medication error.

If any medication error occurs in the course of the study, then the Investigator or other site personnel informs the appropriate AstraZeneca representatives within 1 day i.e., immediately but **no later than 24 hours** of when he or she becomes aware of it.

The designated AstraZeneca representative works with the Investigator to ensure that all relevant information is completed within 1 or 5 calendar days if there is an SAE associated with the medication error (see Section 6.4) and within 30 days for all other medication errors.

## 7 INVESTIGATIONAL PRODUCT AND OTHER TREATMENTS

### 7.1 Identity of investigational product(s)

Investigational product	Dosage form and strength	Manufacturer
dapagliflozin/saxagliptin	film-coated tablets, 10 mg/5 mg	AstraZeneca

### 7.2 Dose and treatment regimens

The IP should be taken once daily at approximately the same time of the day during the study period. The IP should not be altered (eg, crushed, put in another vehicle) and should not be given by nasogastric tube or other routes.

### 7.3 Labelling

Labels will be prepared in accordance with Good Manufacturing Practice (GMP) and local regulatory guidelines. The labels will fulfil GMP Annex 13 requirements for labelling.

### 7.4 Storage

All study drugs should be kept in a secure place under appropriate storage conditions. A description of the appropriate storage conditions is specified on the investigational product pack label.

### 7.5 Compliance

The administration of all study drugs (including investigational products) should be recorded in the appropriate sections of the eCRF. Subjects will be asked to return all unused investigational product and empty packages and bottles to the clinic at each visit. The subject will be asked about compliance at each study visit; compliance will also be assessed based on returned tablet counts. Tablet counts will be recorded in the eCRF. Subjects judged to be non-compliant (defined as taking less than 80% or more than 120% of the prescribed dose of investigational product) may continue in the study, but should be counselled on the importance of taking their study medication as prescribed.

### 7.6 Accountability

Study drug will not be distributed to the study site until the contract is concluded between the study site and AstraZeneca/Delegate. The Investigator/ Site is responsible for managing the study drug from receipt by the institution until the return of all unused study drug to AstraZeneca/delegate. AstraZeneca will provide the study documents 'Procedures for drug

accountability' and 'Procedures for drug storage' which describes the specific requirements. The investigator(s) is responsible for ensuring that the subject has returned all unused study drug.

## **7.7 Concomitant and other treatments**

Changes in concomitant medication should be avoided during study participation, with the exception of situations defined in this protocol, but medication, which is considered necessary for the subject's safety and well-being, may be given at the discretion of the investigators, who must decide if the subject should remain in study or need to be dismissed from study due to subject's safety or interference with study objectives.

The administration of all medication must be recorded in the appropriate sections of the electronic case report form (eCRF) with trade names, dosages, dates of starting and ending of medication and reason for therapy. If the patients glycemic status remains uncontrolled (HbA1c  $\geq 9\%$ , FBG  $\geq 240$  mg/dl (confirmed on readings taken on 2 consecutive days)

After having completed or discontinued the study, investigational product will be discontinued from sponsor but subjects will receive usual care and antidiabetic agents according to the investigator's judgement and according to local medical practice.

### **Prohibited Therapies**

- Weight loss medication, including but not limited to mazindol, sibutramine, phentermine, orlistat, rimonabant, benzphetamine, diethylpropion, methamphetamine, and/or hendimetrazine
- Antiviral drugs (delavirdine, indinavir, nelfinavir, ritonavir, saquinavir)
- Treatment with systemic glucocorticoids equivalent to oral prednisolone  $\geq 10$  mg (betametasone  $\geq 1.2$  mg, dexamethasone  $\geq 1.5$  mg, hydrocortisone  $\geq 40$  mg) per day (two temporary periods of higher daily doses for no longer than 7 days each are allowed).
- Anti-diabetic agents except for the study medication, a basal anti-diabetic agents medication and rescue therapies (Anti-diabetic agents planned to be stopped for wash-out are allowed to be used until the beginning of wash-out period. After completion of the treatment period, alternative anti-diabetic treatment will be initiated according to standard medical practice.)

#### **7.7.1 Other concomitant treatment**

Other medication other than that described above, which is considered necessary for the subject's safety and wellbeing, may be given at the discretion of the Investigator and recorded in the appropriate sections of the Case Report Form.

## 8 STATISTICAL ANALYSES BY ASTRAZENECA

This is an India regulatory requirement study. Objective is to establish that FDC of Dapagliflozin 10mg / Saxagliptin 5 mg is a safe treatment option in Indian T2DM patients. This study is planned as prospective study on 200 patients in single arm open label study. CCI

Data will be summarized using descriptive statistics. Continuous variables will be summarized using the number of observations, mean, SD, median, and range as appropriate. Categorical values will be summarized using the number of observations and percentages as appropriate.

The safety analysis population will include all patients who sign the ICF and receive at least one dose of study medication.

The safety analysis population is also applicable to the efficacy analysis, and any efficacy measurements collected before the study medication discontinuation will be included. Last on treatment observation will be carried forward to impute the missing data at week 24.

Any AE occurring within 2 weeks of discontinuation of investigational product (ie, the last dose of study medication) will be included in the AE summaries. Any events in this period that occur after a patient has received further therapy for (following discontinuation of study drug) will be flagged in the data listings. Adverse event rates shall be stratified by age/gender/baseline medications. Annualised event rate shall also be presented in addition to the incidence rate during the study. Mean change in HbA1C from baseline to 6 months for patients will be analysed using paired t test / Wilcoxon signed-rank test at 5% level of significance.

The study is designed in accordance with the Health Authority requirements in India. It is intended to provide information regarding the safety profile for patients in India, and will contribute additional information to the overall safety profile of Dapa-Saxa FDC. Due to the small sample size, this study should not be directly compared to the data from any other country.

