### Statistical methods

The primary objective of the study is to characterize the safety of fixed dose combination of Dapa/Saxa 10 mg/5 mg in Indian T2DM patients. This is a regulatory requirement to establish that FDCs are safe when used in combination in addition to the data available on individual components. As per the clinical data, based on investigator's assessment incidence of adverse events related to FDC **CCI**

Number and percentages of Incidence of adverse events will be presented, stratified by age/gender/baseline medications. Annualised event rate shall also be presented in addition to the incidence rate during the study. Mean change in HbA1C from baseline to 6 months for patients will be analysed using paired t test / Wilcoxon signed-rank test at 5% level of significance.

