## **1.2 Rationale for study design, doses and control groups**

This study is designed to generate local Indian safety evidence for Dapa/Saxa 10 mg/5 mg FDC as per local health regulatory request. Both dapagliflozin and saxagliptin are approved in India for clinical use as individual therapy for managing T2DM patients. This study is to provide safety data when both molecules are administered as FDC formulation. This is a single arm study and no control group is planned.

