### **Potential benefits to subjects**

All subjects will receive active antihyperglycemic therapy of dapagliflozin /saxagliptin as fixed dose combination; global studies have established the the risk-benefit profile for the individual components, but the safety for the fixed dose combination needs to be confirmed in an Indian phase IV study. In this study, the doses of Dapa/Saxa 10 mg/5 mg FDC was chosen to provide

efficacy in reducing hyperglycemia while mitigating the potential for AEs, based on previous clinical experience. In addition, dapagliflozin decrease body weight (or prevent weight gain) as well as lower blood pressure (BP) especially in subjects with elevated baseline BP.

Subjects are also expected to receive benefit in the form of increased medical care/attention when participating in study procedures, which includes at least 4 clinic visits with at least 4 physical examinations over the 24-week study.

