## 2 STUDY OBJECTIVES

### 2.1 Primary objective

Primary Objective:	Outcome Measure:
To describe the adverse events profile of dapagliflozin + saxagliptin fixed dose combinations in Indian T2DM patients at 24 weeks.	
 
• Adverse Events (AEs) including Serious adverse events (SAEs), AEs leading to discontinuation (DAE) and adverse events of special interest (volume depletion, renal events, major hypoglycaemic events, fractures, urinary/genital tract infections diabetic ketoacidosis, amputations and hospitalization for heart failure)
 
• Safety laboratory values
 
• Electrocardiogram (ECG)
 
• Vital Signs (pulse and BP)
 
• Physical examination
 

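### Section 8 sets out to establish that the combination is safe, but the stated objective and the visible design support only a description of adverse events

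*Protocol*

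**What the plan says.** The protocol words its main purpose in more than one way.

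- Section 2.1 gives the formal primary objective: "To describe the adverse events profile of dapagliflozin + saxagliptin fixed dose combinations in Indian T2DM patients at 24 weeks". The objectives table in the synopsis says the same without the time point.
- The synopsis, under Duration of treatment and again at the start of Statistical methods, uses the verb *characterize*. Statistical methods then adds: "This is a regulatory requirement to establish that FDCs are safe when used in combination in addition to the data available on individual components".
- Section 1.3, under Potential benefits to subjects, says "the safety for the fixed dose combination needs to be confirmed in an Indian phase IV study".
- Section 8 opens with the strongest form: "Objective is to establish that FDC of Dapagliflozin 10mg / Saxagliptin 5 mg is a safe treatment option in Indian T2DM patients". The same section closes by saying that the study is meant to inform on the safety profile in India and add to what is known, and that its small size rules out direct comparison with data from other countries.

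On design, Section 1.2 says "This is a single arm study and no control group is planned", and Section 8 says "This study is planned as prospective study on 200 patients in single arm open label study".

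On analysis, the synopsis says "Number and percentages of Incidence of adverse events will be presented, stratified by age/gender/baseline medications", and Section 8 says "Categorical values will be summarized using the number of observations and percentages as appropriate". Section 8 also promises annualised event rates. The only significance test in the readable text is for change in HbA1c, a secondary outcome.

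**The concern.** To establish that a treatment is safe is to reach a conclusion, and a conclusion needs a standard that the data could fail to meet. To describe an adverse event profile needs no such standard. Section 8 states the first as the objective, while Section 2.1 and the readable analysis deliver the second.

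This matters because the study answers a regulator's request for safety data on the combination. The special-interest list includes ketoacidosis, amputation and hospitalisation for heart failure. Section 3.2 excludes patients with a history of ketoacidosis or of heart failure, which makes low counts of those events more likely. A table showing 0 cases, 0% and an annualised rate of 0, set beside an objective to establish safety, invites the reading that safety has been shown. A zero count in 200 patients is much weaker evidence than that.

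**Working it through.** **Wording, side by side**

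| Place in the protocol | Verb | What it is applied to |
|---|---|---|
| Synopsis objectives table; Section 2.1 | describe | the primary objective |
| Synopsis, Duration of treatment and Statistical methods | characterize | the study or its primary objective |
| Synopsis, Statistical methods, following sentence | establish | the regulatory requirement |
| Section 1.3 | confirm | background rationale |
| Section 8, opening | establish | the objective |
| Section 8, closing | provide information | the intent of the study |

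Only the opening of Section 8 makes establishing safety the objective. It disagrees with Section 2.1 and with the end of its own section.

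**Inputs**

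- n = 200, single arm (Section 8).
- Treatment for 24 weeks (synopsis; Section 4).
- Denominator: every patient who consented and took at least one dose (Section 8). All 200 are assumed to be dosed.
- True event risks: none in the readable text, so a range is assumed.

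The figure of 200 cannot be reproduced. The readable text gives no expected incidence, precision target or threshold, and redactions stand where these would be.

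**What a zero count excludes**

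The exact (Clopper-Pearson) upper limit for 0 of n is 1 − a^(1/n), with a = 0.025 for the two-sided 95% limit and a = 0.05 for the one-sided limit.

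- Two-sided: 1 − 0.025^(1/200) = 1.83%.
- One-sided: 1 − 0.05^(1/200) = 1.49%. The rule of three gives 3/200 = 1.5%.

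On the annualised scale, full follow-up gives 200 × 24/52 = 92.3 patient-years. Zero events then gives an upper limit of −ln(0.025)/92.3 = 4.0 per 100 patient-years (two-sided), or −ln(0.05)/92.3 = 3.2 (one-sided).

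**Chance of seeing no case of one event type**

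P(0) = (1 − p)^200.

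| Assumed 24-week risk p | P(no case in 200) |
|---|---|
| 0.1% | 82% |
| 0.2% | 67% |
| 0.3% | 55% |
| 0.5% | 37% |
| 1% | 13% |
| 1.5% | 5% |

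The break-even point, where the event is as likely to be missed as seen, is p = 1 − 0.5^(1/200) = 0.35%.

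**How many patients a zero count would need**

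To exclude risk p with zero events at one-sided 95%, n is ln(0.05)/ln(1 − p), rounded up: 299 for 1%, 598 for 0.5% and 2,995 for 0.1%.

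**The case against.** The strongest defence is that the protocol already limits itself. Its formal objective is descriptive, the synopsis states the objective as characterizing safety, and Section 8 ends with modest statements of intent and an admission of small size. In the synopsis, *establish* belongs to the regulator's requirement, and *confirm* in Section 1.3 is rationale. All of that stands. It narrows the point to the opening of Section 8, with the synopsis sentence needing only alignment. It does not remove the point, because two statements of the objective still disagree.

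A reader might infer that there is no threshold or bound anywhere, so that no result could count against the safety claim. The documents do not support that. In Section 8 a redaction directly follows the sentence on 200 patients. In the synopsis another falls where an expected incidence of related events would stand. The SAP is also not at hand. A precision target or interval may exist in any of these places. For the same reason, the absence of confidence limits from the protocol is not a finding by itself.

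A reader might also infer that rare special-interest harms will probably be missed. For one event type this holds only below about 0.35%. At 1% the chance of at least one case is 87%. For several event types together it holds less often. With three independent types at 0.1% each, the chance of seeing none of them is 0.8186³ = 55%; at 0.2% each it is 30%, and at 0.5% each 5%. The readable text gives no rates, so which events lie in which range is unknown.

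It is also tempting to shrink the sample for dropout. If 160 patients contributed (an assumed 20% loss), the two-sided limit would be 1 − 0.025^(1/160) = 2.28%. But everyone dosed stays in the safety population, so treating those who leave early as contributing nothing overstates the loss.

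**Conclusion.** The point holds as a conflict over what the study may conclude. The opening of Section 8 promises a finding of safety, whereas Section 2.1, the synopsis objective and the close of Section 8 promise a description. The visible design (200 patients, no control group, counts, percentages and annualised rates) can deliver only the description. Redacted text might justify the sample size, but it would leave the readable sentences in conflict.

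On size, even the most favourable count, 0 of 200, is compatible with a 24-week risk of up to 1.8% (two-sided 95%; 1.5% one-sided). These limits assume that 200 patients are dosed and treat each patient as one binary outcome over 24 weeks. They do not depend on an assumed event rate; the 0.35% break-even is a statement about assumed risks. The data remain usable. What needs correcting is the claim attached to them.

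**What to change.** 1. In Section 8, replace the sentence on establishing safety with the Section 2.1 objective, and align the synopsis sentence on the regulatory requirement with it.
2. Show exact 95% limits beside the percentages for special-interest adverse events, including those with no cases, unless the SAP already provides them.
3. State in Section 8 that 0 of 200 excludes only risks above about 1.8% (two-sided 95%).
4. If the claim to establish safety is to stay, name in advance the event or events it rests on and an acceptable upper limit that a result could fail. By the figures above, a zero count in 200 cannot exclude a 1% risk, so the limit would have to suit the sample size.

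The cost is a wording change and at most one extra table column, with no added patients, visits or procedures. The downside is a more modest headline claim.
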